#### Study Dates and Day of Assessment or Event

Study Day and Day of Assessment or Event definitions are provided in **Appendix 1**.

#### Incorrect Stratification

If there is any discrepancy between the Interactive Web-based Response System -based and clinical-data-based stratification factor, the clinical-data-based value will be used for efficacy analyses.

### **7.5.5 Subgroup Analyses**

Subgroup analyses will be carried out but only for the primary efficacy endpoint. Each subgroup will be analyzed separately using descriptive statistics. No hypothesis tests will be performed. Subgroup variables that will be examined include:

- Smoking status:
  - Current

- Not Current
- Prior history of anti-TNF (Humira) use for HS indication:
  - Yes
  - No
- AN count at baseline:
  - <= median
  - > median
- Age groups:
  - [18, 65) years
  - [18, 30) years
  - [30, 45) years
  - [45, 65) years
  - [65, 75) years
- Sex groups:
  - Male
  - Female
- Hurley Stage at baseline:
  - Stage II
  - Stage III
- Rescue medication used during the treatment period:
  - Yes
  - No

## 7.6 Pharmacokinetic Analyses

The PK analysis will be performed for subjects in the PK Analysis Set.

Mean trough serum concentrations-time data for samples collected on Days 29, 57, 85, 113, 141, 169, 197, will be tabulated as well as graphically presented as scatter plots. Nominal collection times will be used for graphs.

A subject listing of all concentration-time data following SC injections will be presented by subject and scheduled sample collection time. All concentration data of imsidolimab will be summarized by day and nominal time point using the number of observations, arithmetic mean, SD, coefficient of variation (CV), minimum, median, maximum, geometric mean, and CV of geometric mean. Concentrations that are below the limit of quantitation will be treated as zero for the computation of descriptive statistics.

## 7.7 Immunogenicity Analyses

ADA status and titer values will be listed by subject and time point. ADA incidences (overall, treatment-emergent, and treatment-boosted) will be tabulated as absolute occurrence (n) and proportion (%) of subjects. Descriptive statistics of the titer values by treatment group and visit, where possible, will be provided. Neutralizing antibodies, if assayed and present, will also be summarized. The relationship between changes in PK profile and treatment-emergent positive responses will be evaluated to identify a potential impact ADA on imsidolimab exposure. Box plots of ADA status relative to trough concentrations will be plotted. Where possible, evaluation of ADA impact on efficacy and safety may be performed and summarized separately. All immunogenicity results will be listed.

## 7.8 Biomarker Analyses

Biomarker analyses will be performed by a third party designated by the Sponsor. A separate analysis plan will be created for the biomarker analyses.

## 7.9 Safety Analyses

Safety analyses will be performed using the Safety Analysis Set for data from the placebo-controlled period, and the Extension Analysis Set for data from the extension period. Safety parameters include AEs, exposure, clinical laboratory parameters (hematology, biochemistry, and urinalysis), vital signs, and ECGs. Summaries of safety parameters will be presented overall as well as by treatment group.

### Data Imputation for Adverse Events Summaries by Severity and Relationship to Study Drug

For the AE summaries by relationship to study drug, an AE with a missing relationship to study drug will be deemed as definitely related. Imputed values will not be listed in data listings.

### Use of Data from Unscheduled Assessments for Laboratory, ECG and Vital Sign Summaries (Continuous Parameters)

Data from unscheduled visits will be listed; duplicate unscheduled measurements will not be shown twice. If the data from the scheduled visit is missing, data from unscheduled visits that fall in the visit window of the same scheduled visit will be used. In cases where there are multiple unscheduled visits, the most recent unscheduled visit will be used.

### Data Imputation (All Laboratory, Immunogenicity and Biomarker Summaries)

Laboratory values of ' $>=x$ ' or ' $<=x$ ' will be taken as the value of x in the analyses. If a laboratory value is prefixed with ' $>$ ': the available original value +0.001 will be used for table summaries; if a laboratory value is prefixed with ' $<$ ', then the original value -0.001 will be used in table summaries.

### 7.9.1 Extent of Exposure to Study Medication and Compliance

Descriptive statistics (n, mean, standard deviation, median, minimum and maximum) will be presented for the number of doses received, the number of days of exposure to study treatment, total dose received, total dose expected, and dose intensity by treatment group and summarized separately for placebo-controlled period, extension period, and overall. Dose intensity will be defined for each study period as doses received divided by doses scheduled in the period. In addition to summary statistics on the dose intensity as a continuous variable, this will also be categorized into bins. For the placebo-controlled and extension periods separately: 0-25%, >25%-50%, >50%-75%, >75%-100%, and >100%. For the both periods overall: 0-12.5%, >12.5%-25%, >25%-37.5%, >37.5%-50%, >50%-62.5%, >62.5%-75%, >75%-87.5%, >87.5%-100%, and >100%. Dosing information will be listed by study period and by placebo-controlled period and extension period.

### 7.9.2 Adverse Events

Adverse events will be summarized by the number and percentage of subjects experiencing an event. Tables will show the overall incidence of AEs, and the incidence for each treatment group. All reported AEs will be listed, but only TEAEs will be summarized.

#### Adverse Event Counting Rules:

1. A subject with more than one different adverse event in a particular system organ class (SOC) will be counted only once in the total of subjects experiencing adverse events in that particular SOC.
2. A subject having experienced the same event (AE preferred term) more than once during the study will be counted only once in the number of subjects with that event for counts of subjects or incidence measures.
3. If an event changes in intensity or in seriousness during the study, it will be counted only once with the worst grade and seriousness respectively.
4. If the causal relationship to the study drug is assessed differently, it will be counted only once by considering the “Worst” documented degree of relationship.

A TEAE overview summary table will be provided with the incidences of subjects with at least one TEAE, at least one serious TEAE, at least one TEAE related to study treatment, at least one serious TEAE related to study treatment, at least one TEAE leading to treatment discontinuation, at least one serious TEAE leading to treatment discontinuation, at least one TEAE leading to withdrawal from study, at least one serious TEAE leading to withdrawal from study, at least one severe TEAE, at least one severe study treatment-related TEAE, and number of deaths.

Summary tabulations of the following will be prepared for all subjects, for each treatment, for each primary system organ class, and for each preferred term within a SOC. These will report counts and incidences of these categories:

- All TEAEs
- Study treatment-related TEAEs
- TEAEs leading to discontinuation of study treatment
- TEAEs leading to withdrawal from study
- Serious TEAEs
- Study treatment-related serious TEAEs
- TEAEs by relationship to study treatment
- TEAEs by highest severity and treatment
- Severe TEAEs
- Severe Study treatment-related TEAEs

Supporting data listings will be provided by treatment group, including:

- All adverse events (including any AEs reported in the study)
- Serious adverse events
- Adverse events resulting in study treatment discontinuation
- Adverse events resulting in study withdrawal

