Changes in the severity of an AE/SAE will be documented to allow an assessment of the duration of the event at each level of severity to be performed. AEs characterized as intermittent require documentation of onset and duration of each episode.

The Investigator is responsible for appropriate medical care of subjects during the study. After the initial AE/SAE report, the Investigator is required to proactively follow each subject at subsequent visits/contacts. The Investigator also remains responsible for following through with an appropriate health care option for all AEs that are ongoing at the end of the study. The subject should be followed until the event is resolved or stable. If an AE is ongoing at the end of study, the follow-up duration is left to the discretion of the Investigator. Follow-up frequency will be performed at the discretion of the Investigator.

Whenever possible, clinically significant abnormal laboratory results are to be reported using the diagnostic that resulted in the clinically significant abnormal laboratory results and not the actual abnormal test.

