#### 9.4.8.1 ADVERSE EVENTS AND SERIOUS ADVERSE EVENTS

A TEAE is defined as:

- A new event that occurs during or after first dose of study treatment or,
- Any event present at Baseline that worsens in either intensity or frequency after first dose of study treatment.

Adverse events will be coded using the MedDRA and only TEAEs will be summarized. Number of events and percentage will be tabulated by preferred term (PT) and primary system organ class (SOC). Multiple occurrences of an AE for a subject will only be counted once per primary SOC and PT. Percentages will be determined relative to the subjects in the Safety Analysis Set for the given treatment arm.

If the intensity or seriousness of the AE changes, the overall intensity or seriousness will be the maximum intensity or seriousness of the multiple occurrences. The TEAEs, SAEs, TEAEs leading to treatment discontinuation, and TEAEs leading to withdrawal of subject will be tabulated for each treatment arm.

All AE data will be listed for each subject.

Summaries over SOC and PT of TEAEs, TEAEs leading to death, SAEs, and TEAEs that led to discontinuation from the study or study treatment will be presented by treatment. Summaries will also be presented by relatedness to the study treatment and the severity of the TEAE.

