### 6.6.3 Adverse Events

AEs experienced by the subjects will be collected throughout the entire study and will be coded using the latest version of the MedDRA specified in the approved Data Management Plan. Analysis of adverse events will be carried out on the Safety Analysis Set during the placebo controlled period and the Extension Analysis Set for the extension period.

An adverse event is considered treatment-emergent if the date of onset is during or after first dose of study treatment, or if the AE present at baseline that worsens in either intensity or frequency after first dose of study treatment. An adverse event that begins on the same date as the first dose of study treatment is treatment-emergent if the AE begins on or after the time of first dose or if the time of AE onset is unknown.

The severity of AEs will be evaluated as “Mild”, “Moderate”, and “Severe” using the criteria specified in [Section 8.2.1.3.1](#) of the study protocol.

AEs will be classified as related, possibly related, unlikely to be related, or unrelated to study treatment using the criteria specified in [Section 8.2.1.3.2](#) of the study protocol.

Adverse events will be categorized as serious or non-serious using the definition specified in [Section 8.2.1.2](#) of the study protocol.

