8. Adverse event	Treatment-emergent adverse event	
If the AE start date is partial/missing, then
 
 
If AE start date is completely missing, then the AE is considered as treatment-emergent.
 
If both AE start month and day are missing and AE start year is the same or after the first dose year, then the AE is considered as treatment-emergent.
 
If AE start day is missing and AE start year and month are the same or after the first dose year and month, then the AE is considered as treatment-emergent.
 

Category	Description	Data Handling Rules
		Missing/incomplete (partial) AE start and end dates will not be imputed for data listings.
	Assignment of TEAE to Placebo-Controlled vs. Extension and Follow Up Period	Report the TEAE in placebo-controlled period if AP01SDT < AESTDTC; Else report the TEAE in extension and follow-up period if AP02SDT < AESTDTC
	Missing relationship to study drug	For TEAE summary by relationship, a TEAE with a missing relationship to study drug will be considered as related.
9. Efficacy	Change from baseline	Endpoint value at Week x – endpoint value at baseline
	Percent change from baseline	(Endpoint value at Week x – endpoint value at baseline)/ endpoint value at baseline
	Scoring rules for DLQI questionnaires	
 
• If one question left unanswered, assign a score of 0 for that question.
 
• If two or more questions are left unanswered the questionnaire is not scored.
 
• For question 7, 
 
◦ “Yes” is assigned a score of 3
 
◦ “Not Relevant” is assigned a score of 0
 
◦ “No” and “A lot” is assigned a score of 2
 
◦ “No” and “A little” is assigned a score of 1
 
 
 

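### An adverse event that starts on placebo and worsens after the Week 16 switch to imsidolimab is tabulated once, at its worst grade, in the placebo-controlled period, and is left out of the extension tables

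*SAP*

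**What the plan says.** Four rules bear on this.

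- **Grading.** Rule 3 of the Adverse Event Counting Rules in SAP 7.9.2 reads: "If an event changes in intensity or in seriousness during the study, it will be counted only once with the worst grade". The sentence goes on to treat seriousness likewise. Rule 4 covers causality: "If the causal relationship to the study drug is assessed differently, it will be counted only once", at the worst relationship documented. Protocol 9.4.8.1 matches rule 3: when intensity or seriousness changes, "the overall intensity or seriousness will be the maximum intensity or seriousness of the multiple occurrences". None of these is confined to a study period.
- **Period.** SAP 6.6.1 refers period assignment to Appendix 1, where item 8 says: "Report the TEAE in placebo-controlled period if AP01SDT < AESTDTC; Else report the TEAE in extension and follow-up period if AP02SDT < AESTDTC". The test uses the event's start date only, and its if/else form gives an event at most one period.
- **Emergence.** Under SAP 6.6.3 an event is treatment-emergent if it starts during or after the first dose of study treatment, or "if the AE present at baseline that worsens in either intensity or frequency after first dose of study treatment". Protocol Section 6 counts placebo as study treatment, so the reference point for a placebo subject is Day 1.
- **Switch.** Every placebo subject who continues starts imsidolimab at Day 113, as Arm 3A or 3B. SAP 6.6.3 and 7.9 analyse adverse events on the Safety Analysis Set for the placebo-controlled period and on the Extension Analysis Set for the extension.

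**The concern.** Each rule is ordinary on its own. Together they join an onset date from one treatment to a grade from another. A placebo subject's event can begin mild before Day 113, become severe or serious on imsidolimab, and be reported as a severe or serious event on placebo. The extension tables, which are meant to describe what happened to these subjects on imsidolimab, would not contain it.

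Safety is a secondary objective (Protocol 3.2), and Protocol 10.1.6 requires no data and safety monitoring board. The summary tables also feed the Week 16 primary analysis, which goes to the sponsor's executive management to inform development decisions (SAP 3.4). That analysis waits until every subject has completed Week 16 or left. Earlier enrolees will by then have extension data, and the SAP does not say that the data cut-off is applied to each subject at Week 16. The problem can therefore enter the first readout.

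**Working it through.** The plan states no figure on this point, so there is none to reproduce. The check traces events through the rules.

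**Inputs.** Period starts are Day 1 and Day 113, and the end-of-study visit is Day 281 (Protocol 1.3). There are 40 planned placebo subjects with 10% discontinuing before Week 16 (Protocol 9.2, SAP 3.5). The SAP does not define AP01SDT and AP02SDT; I read them as the start dates of the two periods.

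**Step 1: period by onset day.** The literal rule is item 8 as printed, comparing dates only. The evidently intended rule adds an upper bound: placebo-controlled from Day 1 to before Day 113, extension from Day 113.

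| Onset day | Literal rule | Intended rule |
|---|---|---|
| 1 | neither period | placebo-controlled |
| 2, 60, 100, 112 | placebo-controlled | placebo-controlled |
| 113, 114, 150, 200, 280 | placebo-controlled | extension |

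Read literally, the first condition is true for every onset after Day 1, so the second branch is never reached. That is a separate and larger defect. Repairing it does not settle the present point, because assignment would still follow onset alone.

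**Step 2: one placebo subject, one record, mild from Day 100, severe from Day 150.**

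| | Placebo-controlled table | Extension table |
|---|---|---|
| Current rules, literal or intended | severe | absent |
| Grade limited to period, worsening counted after the switch | mild | severe |

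Seriousness (rule 3) and relationship (rule 4) behave in the same way.

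**Step 3: size per event.** The denominator is the planned placebo column, assuming that all 40 are dosed. One subject whose event becomes severe or serious only after the switch moves that placebo rate by 1/40 = 2.5 percentage points; two move it by 2/40 = 5.0; three by 3/40 = 7.5. About 40 × 0.9 = 36 placebo subjects are expected to reach the switch, and the time in which a worsening can be carried back is 281 − 113 = 168 days, or 24 weeks. The documents give no rate for such events, so no expected total follows.

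**Step 4: the other arms.** The same rules apply to Arms 1 and 2. An event that starts before Day 113 and worsens later is carried back at its worst grade into that arm's placebo-controlled column. There it stays under imsidolimab, but it still includes grades from after the randomised period against placebo.

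**The case against.** The strongest reply is that the SAP can be read sensibly as it stands. Section 7.9 speaks of data from each period, and 6.6.1 of the period in which events occurred, so a grade reached on Day 150 is arguably not placebo-period data. Protocol 9.4.1 re-calculates baseline for former placebo subjects in Extension Analysis Set analyses, and SAP Section 6 defines an imsidolimab baseline without excluding adverse events. On that basis a reader should not infer that worsening after the switch could never count as treatment-emergent. What stands is that the general text leaves room for the right answer. But no adverse-event passage applies period-limited grading or the imsidolimab baseline to events, and the specific rules (start date for period, whole study for grade) point the other way.

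A second reply concerns the eCRF, which is not in the documents. If sites open a new dated record at each worsening, the intended period rule would put that record in the extension. However, Protocol 8.2.1.5 sends updated information to the original eCRF entry, and rule 3 would still count the event once. Protocol 8.2.1.4 does say "Changes in the severity of an AE/SAE will be documented", but whether each change carries a date in the dataset needs confirming.

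A third reply concerns direction. A reader might infer that both effects favour imsidolimab. That is true of the placebo column and the extension tables taken alone. It is not established for the randomised comparison, because Arms 1 and 2 are inflated by the same mechanism and the difference could move either way or hardly at all.

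Finally, the event is not hidden. All adverse events and all serious adverse events are listed by subject, so the distortion is confined to the summary tables.

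**Conclusion.** The point holds as a defect in the tabulation rules. For Arms 3A/3B, worsening on imsidolimab of an event that began on placebo is charged to placebo and omitted from the extension treatment-emergent tables. The conclusion assumes that a worsening is recorded by updating one record with its original start date. It does not depend on whether item 8 is read literally or as intended.

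The size is 2.5 percentage points of the placebo severe or serious rate for each subject whose event crosses that threshold only after the switch. Multiplying this by an assumed frequency would go beyond the documents, and a mild event that becomes moderate changes neither rate. The net effect on the comparison with placebo is unknown in sign and size.

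Nor should a reader take the adverse-event table as the only randomised safety evidence: laboratory data, vital signs and ECGs are also summarised by arm. The change is worth making because a stated rule gives a wrong attribution and the remedy is cheap.

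**What to change.** Revise SAP 6.6.3, 7.9.2 and Appendix 1 item 8 together, in the same edit that bounds the placebo-controlled condition above by the extension start.

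1. In placebo-controlled tables, for all arms, use the worst grade, seriousness and relationship recorded before the first extension dose.
2. For Arms 3A/3B, count an event that is ongoing at the first imsidolimab dose and worsens in intensity or frequency afterwards as an extension-period treatment-emergent event at the worsened grade, using the imsidolimab baseline that SAP Section 6 already defines.
3. If worsening in seriousness is also to count, declare it in SAP Section 8, because Protocol 9.4.8.1 names only intensity and frequency.
4. State where post-Week-16 worsening in Arms 1 and 2 is shown, so that step 1 does not drop it from both sets of tables.
5. Confirm that the adverse-event eCRF holds the date of each severity change, in line with Protocol 8.2.1.4.

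The cost is SAP wording and a change to the adverse-event dataset derivation. If step 5 is confirmed, no new data are needed for grade; the dates of changes in seriousness and relationship should be checked at the same time. The downside is that one clinical event can appear in both period tables, which needs a footnote.

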### 7.9.3 Laboratory Data

Summary statistics (n, mean, median, standard deviation, minimum, and maximum) for the baseline assessment and for the observed value and change from baseline at each post-baseline visit for scheduled lab assessments of continuous laboratory variables will be tabulated. Shift tables (e.g., tables that show the number of subjects who are low, normal, or high at baseline versus each post-baseline scheduled assessment) will be produced.

If there are multiple laboratory values for the same parameter at a given visit, the last value will be chosen for analysis.

All data will be displayed in patient data listings for Safety Analysis Set.

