### 5.1 INCLUSION CRITERIA

To be eligible to participate in this study, a subject must meet all of the following criteria, either at the screening and Day 1 visits or only at one of the specified visits (screening or Day 1) as noted in the criterion:

1. Male or female aged 18 to 75 years (inclusive) at the time of signing informed consent.
2. Clinically confirmed diagnosis of active HS with a disease duration of  $\geq$  6 months before Day 1 (information obtained from medical chart or subject's physician, or directly from the subject).
3. HS lesions present in at least 2 distinct anatomical areas, 1 of which must be Hurley Stage II (ie, single or multiple, widely separated, recurrent abscesses with tract formation and cicatrization) or Hurley Stage III (ie, diffuse or near-diffuse involvement, or multiple interconnected tracts and abscesses across the entire area).
4. Total AN count  $\geq$  5.
5. Subject has  $\leq$  20 draining fistulas
6. Stable HS for at least 6 weeks prior to Day 1 visit as determined by the Investigator through subject interview and review of medical history.
7. Agree to daily use (and throughout the study) of one of the following over-the-counter treatments on their body areas affected with HS lesions: chlorhexidine gluconate, triclosan, benzoyl peroxide, dilute bleach in bathwater, or soap and water.
8. Meet the following laboratory criteria at screening:
  - a) Hemoglobin  $\geq$  90 g/L ( $\geq$  9 g/dL)
  - b) White blood cell count  $\geq$   $3.0 \times 10^9$ /L ( $\geq$   $3.0 \times 10^3$ /μL)
  - c) Platelets  $\geq$   $100 \times 10^9$ /L ( $\geq$   $100 \times 10^3$ /μL)
  - d) Serum creatinine  $<$  132.6  $\mu$ mol/L ( $<$  1.5 mg/dL)
  - e) Alanine aminotransferase (ALT) and aspartate aminotransferase (AST)  $\leq$  2 upper limit of normal (ULN)
  - f) Total bilirubin  $\leq$   $1.5 \times$  ULN. Subjects with known Gilbert's disease who have serum bilirubin  $<$   $3 \times$  ULN may be included
9. Body weight  $\geq$  40 kg.
10. Contraceptive use by men and women should be consistent with local regulations regarding the methods of contraception for those participating in clinical studies.

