#### 9.4.8.2 12-LEAD ELECTROCARDIOGRAM, VITAL SIGNS, AND CLINICAL SAFETY LABORATORY TESTS

Summaries and listings of data for vital signs and safety laboratory tests result (hematology, biochemistry, and urinalysis) will be presented. Appropriate descriptive statistics will be summarized for the observed value at each scheduled assessment and for the corresponding change from Baseline.

For hematology and biochemistry tests, listings of subject data will also flag up any abnormal or out-of-range values. Clinically significant changes in the laboratory test parameters will be summarized and listed. Hematology and biochemistry data will be reported in System International units.

Descriptive statistics will be used to present the safety outcomes including, weight, BMI, 12-Lead ECG, vital signs, and clinical laboratory test results.

Change from Baseline will also be summarized for vital signs, and clinical laboratory tests results.

All ECG data results (normal/abnormal) will be summarized using frequency and percentage, and parameter values will be summarized descriptively. Clinically significant abnormalities will be presented in by-subject listings.

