#### Abnormal Values

Based upon laboratory normal ranges, laboratory test results will be categorized according to the normal range as low, normal, and high. Subjects with laboratory data outside the normal range will be listed with abnormal values flagged.

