### 7.9.5 Electrocardiogram (ECG)

ECG data (Heart Rate, PR Interval, RR Interval, QRS Interval, QT Interval, and QTcF Interval) will be tabulated with descriptive statistics by visit for both the raw values as well as the changes from baseline.

Number and percentage of subjects with clinically significant abnormalities in all ECG parameters will be summarized for normal, abnormal - not clinically significant and abnormal - clinically significant categories by treatment group. Three-by-three contingency tables will be presented to summarize the shift from the baseline category to the worst post-baseline value. Summary results will include the count and percentage of subjects within each shift category and treatment group.

If there are multiple ECG values for the same parameter at a given visit, the last value will be chosen for analysis.

All ECG data as well as clinically significant abnormalities will be presented in by-subject listings.

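### SAP 7.9.3 omits, without declaring it, the protocol's summary of clinically significant laboratory changes, and its low/normal/high shift table cannot show worsening in subjects already out of range at baseline

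*SAP*

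**What the plan says.** **Protocol.** Section 3.2 makes changes in clinical laboratory parameters part of the secondary safety endpoint. Section 9.4.8.2 adds a specific output: "Clinically significant changes in the laboratory test parameters will be summarized and listed". Inclusion criterion 8 sets the liver limits at screening. ALT and AST may be at most "2 upper limit of normal (ULN"). Total bilirubin may reach 1.5 times ULN, with a wider allowance, below 3 times ULN, for "Subjects with known Gilbert's disease who have serum bilirubin" within that bound.

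**SAP.** Under Abnormal Values (6.6.4), "laboratory test results will be categorized according to the normal range as low, normal, and high". Section 7.9.3 then plans:

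- descriptive statistics, including minimum and maximum, "for the baseline assessment and for the observed value and change from baseline at each post-baseline visit for scheduled lab assessments";
- shift tables, introduced by e.g. and described as "tables that show the number of subjects who are low, normal, or high at baseline versus each post-baseline scheduled assessment";
- listings of all laboratory data. Section 6.6.4 adds that "Subjects with laboratory data outside the normal range will be listed with abnormal values flagged".

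Neither section mentions clinical significance for laboratory results. For ECG the SAP does keep such an output (7.9.5): "Number and percentage of subjects with clinically significant abnormalities in all ECG parameters will be summarized", together with a shift to the worst post-baseline category. SAP Section 8 lists the changes from the protocol, down to the spelling of the global impression questionnaires. It does not list this one.

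**The concern.** There are two linked gaps. First, a summary that the protocol commits to has no counterpart in the SAP, and the section meant to record departures is silent. Second, the categorical summary that remains is a poor substitute. Its categories are set by the normal range alone, and the entry criteria let subjects start in the top category for exactly the tests used to watch for liver effects. Such a subject can be seen to improve but not to worsen in that table.

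At stake is whether the report can say how many subjects in each arm had a material laboratory deterioration, by parameter. With about 40 subjects per arm, a handful of marked rises would be the signal of interest, and a count by arm is the natural way to show it.

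**Working it through.** The documents state no figure for this point, so there is nothing to reproduce. The check sets the passages side by side and enumerates the shift-table cells.

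**Step 1. Commitment against plan.**

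| Output | Protocol 9.4.8.2 | SAP |
|---|---|---|
| Descriptive statistics by visit | yes | yes (7.9.3) |
| Listing with out-of-range flags | yes | yes (6.6.4, 7.9.3) |
| Summary of clinically significant laboratory changes | yes | none |
| Listing of clinically significant laboratory changes | yes | none |
| Low/normal/high shift | not required | yes, as an example (7.9.3) |
| Departure declared in SAP Section 8 | – | no |

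**Step 2. Shift-table cells.** Inputs: the SAP 6.6.4 categories (high means above 1 × ULN) and baseline values that criteria 8e and 8f allow. The post-baseline values are illustrative assumptions.

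| Test | Baseline (× ULN) | Post-baseline (× ULN) | Cell |
|---|---|---|---|
| ALT/AST | 1.5 | 0.8 | high to normal |
| ALT/AST | 1.5 | 1.5 | high to high |
| ALT/AST | 1.5 | 2, 3, 5 or 10 | high to high |
| Bilirubin | 1.5 | 3 | high to high |
| Bilirubin, Gilbert's disease | 2.9 | 6 | high to high |
| ALT | 0.9 | 1.1, 3 or 10 | normal to high |

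No change and a rise to 10 × ULN share a cell for a subject who starts high. A trivial rise and a marked rise share a cell for a subject who starts normal.

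**Step 3. What the descriptive table shows.** Take an arm of 40 (120/3), with one subject rising from 1.5 to 10 × ULN and the other 39 unchanged:

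- maximum change = 10 − 1.5 = 8.5 × ULN;
- mean change = 8.5/40 = 0.21 × ULN;
- median change = 0;
- SD = √[8.5² × (1 − 1/40)/39] = √1.806 = 1.34 × ULN.

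The maximum reveals the rise. It does not tell the reader whether one subject or several worsened.

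**Step 4. Whether the maximum is reliable.** The descriptive table is built on scheduled assessments. SAP 7.9 uses an unscheduled result only when the scheduled one is missing, and 7.9.3 takes the last of several values at a visit. Protocol 8.2.7 has clinically significant values repeated until they resolve or stabilise. A peak found at an unscheduled visit, or followed by a repeat within the same visit, can therefore be absent from the table.

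**Step 5. The adverse event route.** Under protocol 8.2.1.1.1 and 8.2.7, laboratory results that the investigator judges clinically significant are recorded as adverse events, and SAP 7.9.2 tabulates treatment-emergent events by arm. However, protocol 8.2.1.4 prefers the diagnosis to the abnormal test, so cases may spread over several preferred terms. Protocol 8.2.1.1.2 leaves out findings tied to the underlying disease unless they are worse than expected.

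**The case against.** The strongest reply is that worsening is far from invisible. The sentence just before the shift tables in SAP 7.9.3 gives the maximum observed value and the maximum change at each visit. Out-of-range values are flagged and all values are listed. Clinically significant results reach the adverse event tables, which are counted by arm, severity and relationship. The three-category form is only an example, the mock-ups sit in a separate document (SAP Appendix 3) that is not available here, and SAP Section 1 says the plan is to be read with the protocol. Nothing in protocol 9.4.8.2 asks for graded bands.

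Most of this stands. A reader might infer that the SAP keeps nothing but low/normal/high shifts, or that a subject who enters high can never be shown to worsen anywhere in the report. The documents do not support either reading: that limitation belongs to the shift table alone. Nor do they give any share of subjects with a high baseline. The entry limits apply at screening, whereas baseline is the last value before first dose (SAP Section 6), so the number could be very small. Graded bands are a recommendation, not a protocol obligation.

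The reply does not supply the missing output. A maximum is not a count, a listing gives no comparison between arms, and the adverse event tables are not organised by laboratory parameter. Reading the SAP with the protocol does not help either, since the SAP gives no definition, source or layout for the protocol's summary.

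**Conclusion.** The concern holds in a limited form. The undeclared omission is plain from the texts and rests on no assumption about subject numbers. The shift-table limitation is also certain, provided the tables are produced in the form the SAP gives as its example. Together they leave the plan as written without a count, by arm and by parameter, of subjects whose laboratory values worsened materially.

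The size cannot be stated: the documents do not say how many subjects begin out of range or how many will have marked rises. The consequence is a less informative safety report, not a concealed harm, because other planned outputs can show individual marked rises. It does not touch the primary efficacy analysis. It should be corrected because laboratory change is a named safety endpoint and the correction is cheap.

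**What to change.** In SAP 7.9.3:

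1. Restore the protocol 9.4.8.2 summary and listing of clinically significant laboratory changes: number and percentage of subjects by arm and, where the source allows, by parameter. State the source. The documents describe a clinical-significance entry in the eCRF for ECG (SAP 6.6.6) but none for laboratory results, so one option is investigator-judged significant results recorded as adverse events. If the output is not to be produced, or is held to be met by the adverse event tables, say so and justify it in SAP Section 8.
2. For ALT, AST, ALP and total bilirubin, add a shift table by arm from baseline band to worst post-baseline band, unscheduled values included, in multiples of ULN (for example up to 1, >1–2, >2–3, >3–5, >5). Do the same with bands below the lower limit of normal for haemoglobin, leukocytes, neutrophils and platelets. These are reporting categories only and change no eligibility, dosing or stopping rule.

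The cost is SAP wording and a few extra tables. Item 2 uses numeric results already collected. Item 1 needs a decision on where the clinical-significance judgement comes from, because laboratory values alone do not supply it.
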